6.5. Concomitant Therapy

Concomitant medications will be recorded from 45 days prior to first vaccination until 10 months after the final vaccination. An initial review of past medical history will include a review of medications. Information pertaining to receipt of non-study vaccines, research agents, immunoglobulin preparations, immunosuppressive medication, antiretroviral drugs, and any blood products will be elicited at study visits and recorded in source documents.

To ensure appropriate medical follow-up for study participants, information regarding concomitant medications used in association with an AE will be collected and recorded in the source documents.

Study participants can receive medications such as acetaminophen, non-steroidal anti-inflammatory drugs (NSAIDs), or antihistamines as required, although they must be documented.

6.6. Dose Modification

Excluding the aforementioned study arm dose-escalation of ALFQ, no modification of dosage for any of the vaccine products will be allowed in this study.

6.7. Treatment After the End of the Study

There is no plan to continue with study injections after the end of the study.

7. DISCONTINUATION CRITERIA

Each participant has the right to withdraw from the study at any time for any reason without penalty. In those cases where a "withdrawal of consent" is requested by the participant, documentation of the withdrawal of consent and the reason(s) for the request will be captured in the participant's clinical research records and/or on the status change CRF. Although the participant is not obligated to give reason(s) for withdrawing, the investigator should make a reasonable effort to ascertain the reason(s) while fully respecting the participant's rights. The participant will also be asked if she/he will agree to complete the clinical assessments listed for the study termination/exit visit.

7.1. Screening Failures

Screen failures are defined as subjects who consent to participate in the clinical study but either are deemed not eligible or are not subsequently randomized. The investigator will ensure that the

following information is collected for each screen failure—demographic information, and the reason for the screen failure.

7.2. Discontinuation of Study Intervention

Under certain circumstances, a participant will be terminated from participating in further vaccinations. These specific experiences include:

- Investigator's clinical judgment is that it is in the best interest of the subject
- Confirmed diagnosis of HIV
- Pregnancy
- Clinically significant Type 1 hypersensitivity associated with vaccination
- Serious concomitant illness that is not expected to resolve prior to the next scheduled vaccination or will require contact isolation during the next scheduled vaccination.
- Treatment with chronic systemic glucocorticoids (e.g., prednisone) or other immunomodulators other than NSAIDs for greater than 10 days. Inhaled and topical steroid use is not exclusionary
- Need for concomitant vaccine that requires discontinuation
- After initial vaccination, missing any subsequent vaccination by more than 15 days

Participant's request Immediate Early Discontinuation will occur:

1. Upon learning of pregnancy;
2. Due to an SAE that is believed to be related to study vaccination, including:
 - a. Any Grade 3 systemic adverse reaction that is assessed as related to the study agent,
 - b. Any Grade 4 AE assessed as related to the study agent, or
3. If a participant develops infection with HIV-1.

Each case will be reviewed by the Protocol Safety Review Team (PSRT) to assess impact on study conduct overall and continuation of individual participants with referral to the U.S. FDA and WRAIR IRB, in consultation with the study sponsor.

7.2.1. PSRT

The PSRT will include the following:

- Sponsor's Medical Expert or designee
- HIV Vaccine Product Manager or designee
- ORA Pharmacovigilance (PVG) Physician
- PI or designee
- Independent Safety Monitor (ISM)

Additional PSRT participants may include, as needed, the following:

- Associate Investigators
- Clinical research nursing staff
- Laboratory directors

- Data management and regulatory staff
- DAIDS Medical Officer

PSRT conference calls or meetings will require, at minimum, the participation of the Sponsor's Medical Expert or designee, ISM, and the PI or designee. The WRAIR IRB will be notified of the decisions taken by the PSRT if they involve suspensions, clinical holds (voluntary or involuntary), or terminations of this research in accordance with [Table 8](#). The USAMRDC ORA PSSO will be responsible for safety reporting to the U.S. FDA.

The DAIDS Medical Officer will serve in a consultant role on the PSRT but is not required for PSRT or any other protocol team decisions.

Participants who are discontinued from additional study vaccinations will be discussed with the PSRT to determine the duration, if any, of follow-up visits to further evaluate safety and monitor adverse experiences.

Wherever possible, the tests and evaluations listed for the termination visit should be carried out if the subject refuses follow-up according to the protocol visit schedule.

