B-Cell Analysis		17	17	17	17	17	17		17	17	17	17	
Multiparameter Flow Cytometry		17	17	17	17	17	17		17	17	17	17	
Innate Cell Analysis		17	17			17			17	17	17	17	
Transcriptomics		2.5	2.5	2.5	2.5	2.5	2.5		2.5	2.5	2.5	2.5	
Additional Immunogenicity Testing		42.5	8.5	8.5	8.5	8.5	8.5		17	25.5	34	34	

Visit Number	0	1	2	3	4	5	6	7	8	9	10 ² /Exit 4	Phone Follow-up #1	Phone Follow-up #2
Visit Type	Screen	V1	Safety & Immun	V2	Safety & Immun	V3	Safety & Immun	Safety & Immun	Safety & Immun	Safety & Immun	MAAE follow-up	MAAE follow-up	MAAE follow-up
Visit Day	-45 to -3	1	15	29	43	57	58-59	64	71	169	337	365	393
Window			± 3d	± 7d	± 3d	± 7d		± 3d	± 3d	± 7d	± 7d	± 7d	± 7d
Visit Week	0	2	4	6	8	8	9	10	24	48	52	56	
Daily Volume (mL) ⁶	23	111.5	85	60.5	85	60.5	19.5	70.5	102	100	108		
Cumulative Volume (mL)	23	134.5	219.5	280	365	425.5	445	515.5	617.5	717.5	825.5		
8-Week Cumulative Volume (mL)						402.5	422	381	483	100	108		

SP = Assay performed from stored plasma; no additional blood volume required

¹ Full physical examination at screening (visit S1) and targeted physical examination at all other visits; Vitals to be collected both pre- and at about 30 minutes post-vaccination at Visit Day 1, 29, and 57.

² Participants will be contacted for the unblinding visit after the clinical data is locked.

³This includes unsolicited AEs which will be collected until 28 days post each vaccination.

⁴Medically Attended AEs will be followed through the end of the study, a full 12 months following the last vaccination. After clinic visits end, follow-up for MAAEs will occur by monthly phone calls for two months.

For those participants who are unable to continue participation in the study, but who do not withdraw consent, an exit visit will be conducted.

⁵ Research labs may be performed at any visit where sufficient stored samples are available

⁶ Blood volumes for clinical lab assays may be adjusted as long as maximum daily blood volume is not exceeded.

⁷ Pregnancy tests can be conducted at any visit if clinically indicated.

⁸ Any clinically indicated safety labs can be obtained at investigator discretion

^{*}10 mL EDTA verification blood collection for HIV incident case resolution for enrolled participants.

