4.7. End of Study Definition

The end of the study primary completion date is defined as the last subject last visit (LSLV). Each participant will be followed for 12 months after the final vaccination. Follow up includes 10 months of clinic visits and two additional telephone follow up visits at 1-month intervals for a total of 12 months. The completion of laboratory assays and data analysis is anticipated to take up to 5 years from the primary completion date.

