8.2.1.5. Medically Attended Adverse Events (MAAE)

The FDA requests that clinical trials of preventive vaccines with adjuvants such as ALFQ provide for collection and analysis of data relating to MAAEs among subjects in all treatment groups through 12 months or longer following the last study vaccination, due to the theoretical potential for induction of autoimmune or auto-inflammatory diseases.

MAAEs are defined as AEs with medically attended visits including hospital, emergency room, urgent care clinic, or other visits to or from medical personnel for any reason. Adverse events (e.g., abnormal vitals) identified at a routine study visit will not be considered MAAEs. MAAEs include, but are not limited to, PIMMCs.

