8.2.2. Timeframe for Collecting Adverse Event Information

All AEs and SAEs will be collected from the start of treatment until the end of the protocol-defined follow-up period, at the time points specified in Section 1.3, Schedule of Activities. Adverse events and SAEs will be assessed at all study visits, documented in the source records, and recorded on the CRFs using accepted medical terms and/or the diagnoses that accurately characterize the event. All unsolicited AEs will also be collected from at least 28 days after each vaccination. Medical occurrences that begin before the start of study treatment but after obtaining informed consent will be recorded on the Medical History/Current Medical Conditions section of the CRF.

Unsolicited adverse events (AEs) and Medically Attended Adverse Events (MAAEs) will be collected from the day of IP administration and for the next 28 days. The investigator will also document SAEs, MAAEs and AESIs (including PIMMCs) for at least 12 months after subjects receive their last study vaccination.

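### Protocol 7.2.1 lets the PSRT set short or no follow-up after vaccination is stopped, in conflict with the 12-month safety follow-up in 4.7, 8.2.1.5 and 8.2.2

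*Protocol*

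**What the plan says.** Protocol Section 7.2.1 provides that participants "discontinued from additional study vaccinations will be discussed with the PSRT to determine the duration, if any, of follow-up visits", the stated aim being further safety evaluation. No minimum is given.

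Three other sections fix a period:

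- Section 4.7: "Each participant will be followed for 12 months after the final vaccination".
- Section 8.2.2: "The investigator will also document SAEs, MAAEs and AESIs (including PIMMCs) for at least 12 months after subjects receive their last study vaccination".
- Section 8.2.1.5 reports a regulator's request that MAAEs be collected in all treatment groups "through 12 months or longer following the last study vaccination", because adjuvants might in theory induce autoimmune or auto-inflammatory disease.

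Section 7.2 lists the reasons for ending vaccination. Some are reactions to the product: "Clinically significant Type 1 hypersensitivity associated with vaccination", "Any Grade 3 systemic adverse reaction that is assessed as related to the study agent", and related Grade 4 events. Others are not, such as a vaccination missed by more than 15 days, need for another vaccine, pregnancy and HIV.

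On analysis, Table 13 of the Protocol and SAP Section 5.3.1 keep anyone with at least one dose in the Safety population; the SAP adds that some post-dose data must exist. SAP Section 7 leaves the denominator for safety percentages open between non-missing observations and population size. Protocol 9.6.4 and SAP 5.5 rule out imputation and treat missingness as ignorable only below 10% and completely at random.

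**The concern.** The PSRT's discretion in 7.2.1 has no floor, while the duty in 8.2.2 has no exception. For a participant taken off vaccination, any PSRT choice shorter than 12 months sets the two sections against each other, and the reader cannot tell which governs.

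The safety comparison among ALFQ doses is the primary purpose of the trial. Follow-up that may be shortened after a related reaction depends on the outcome under study. The principal investigator and study staff are blinded to dose, so no dose-aware decision is needed for harm to arise: if stopping reactions become more frequent with dose, late follow-up is lost more often in the higher-dose arm, and its count of new late SAEs, AESIs and MAAEs is pulled down. Events that were never ascertained cannot be recovered in the analysis.

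**Working it through.** **The texts side by side.** Take a participant who receives only the Day 1 dose and is stopped at the Day 29 visit.

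- Under 8.2.2, SAE, MAAE and AESI documentation runs to about Day 1 + 365 = Day 366.
- Under 7.2.1, the PSRT may decide that no further visits take place. Observation would then cover 28/365 = 8% of that period.
- Section 8.2.17 follows SAEs and events of special interest already reported until they resolve. It does not provide for finding new ones, and it places no duty on investigators to look for SAEs in former participants.
- Pregnancy (7.2.2) and HIV (7.3) have their own follow-up provisions. Participants stopped for a related reaction or hypersensitivity have none and fall under the open discretion.

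The contradiction is therefore textual and needs no number.

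**The plan's own figure.** The only stated precision for these endpoints is the upper limit of 13.9% for zero events in 20, labelled two-sided 95% (Protocol 9.4, SAP 4.4.1). A two-sided limit is 1 − 0.025^(1/20) = 16.8%; 13.9% is the one-sided value, 1 − 0.05^(1/20). That labelling is a separate matter. If stopped participants left the denominator, the two-sided zero-event limit would rise to 17.6% (n = 19), 18.5% (n = 18) or 20.6% (n = 16). This measures lost precision, not bias.

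**Size of the understatement if they stay in the denominator.** Assumptions, none of them in the documents: a true risk p over 393 days (the day of the last scheduled call), a constant hazard, and k of 20 in an arm stopped with nothing ascertained after day d.

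- Hazard: h = −ln(1 − p)/393. For p = 0.10, h = 0.10536/393 = 0.000268 per day.
- Risk seen by day d: F(d) = 1 − exp(−h·d), so F(29) = 0.0077 and F(57) = 0.0152.
- Expected observed arm risk: [(20 − k)·p + k·F(d)]/20. For k = 1 and d = 29: (1.9 + 0.0077)/20 = 9.54%.

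| k of 20 | d = 29 | d = 57 | Shortfall from 10% (points) |
|---|---|---|---|
| 1 | 9.54% | 9.58% | 0.46 / 0.42 |
| 2 | 9.08% | 9.15% | 0.92 / 0.85 |
| 4 | 8.15% | 8.30% | 1.85 / 1.70 |

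Over the same range of k and d, the shortfall is 0.21 to 0.92 points for a true 5% risk (5.00 − 4.79; 5.00 − 4.08) and 0.84 to 3.67 points for a true 20% risk (20.00 − 19.16; 20.00 − 16.33).

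**Between arms.** If two arms both have a true 10% risk, with 4 stopped in one and 1 in the other at Day 29, the expected false difference is 9.54 − 8.15 = 1.39 points in favour of the arm with more stopping.

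**If stopped participants are at higher risk.** Suppose they carry three times the hazard, so their 393-day risk is 1 − 0.9³ = 27.1%. With k = 4 and d = 29, the true arm risk is (1.6 + 4 × 0.271)/20 = 13.42% and the expected observed risk is 8.46%, a shortfall of 4.96 points. With k = 1 and d = 57 it is 10.85 − 9.72 = 1.13 points.

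The 393-day horizon is slightly long for someone stopped after one dose, whose own 12 months end near Day 366, so these shortfalls are slightly high for that case.

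**The case against.** The strongest reply is that 7.2.1 permits shorter follow-up but does not order it, and that other text limits the damage. Much of this stands.

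- A reader might infer that stopped participants drop out of the primary SAE and AESI endpoints. The documents do not support that. They remain in the Safety population, and the triggering event is recorded and, if an SAE or event of special interest, followed to resolution. Only the ascertainment of new late events is at risk.
- A reader might take the stopped group to be the reactors. Many listed reasons have nothing to do with a reaction.
- A reader might picture the site closing out a reactor on its own. The decision belongs to the PSRT, whose meetings need the Independent Safety Monitor and the Sponsor's Medical Expert or designee; Section 7.2 adds referral to the FDA and IRB in consultation with the sponsor.
- The Table 1 footnote, "For those participants who are unable to continue participation in the study, but who do not withdraw consent, an exit visit will be conducted", concerns people who cannot continue in the study. It is not the route for those stopped only from vaccination.
- Section 8.2.1.5 covers MAAEs only, and 4.7 names no event type. Only 8.2.2 covers SAEs, MAAEs and AESIs together.
- The last sentence of 7.2.1 treats the protocol visit schedule as something a participant may refuse, which suggests that it still applies, and nothing there expressly cancels the calls or the 8.2.2 duty.

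The last item does not settle the matter. It shows a default schedule and an open discretion standing in the same section, and the discretion is not confined to extra visits. Replacement under 7.3.1 while enrollment is open adds participants but does not recover the late follow-up of the person replaced.

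**Conclusion.** The concern holds as a conflict between 7.2.1 on one side and 4.7, 8.2.2 and, for MAAEs, 8.2.1.5 on the other. Its consequence is possible loss of new late SAEs, AESIs and MAAEs in dosed participants taken off vaccination. Because some stopping reasons are vaccine-related reactions, that loss could be informative and could differ by ALFQ dose. It would not be missing completely at random, and the analysis plan has no remedy for it.

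The size is unknown, because neither document gives an expected number stopped. Under the assumed 1 to 4 of 20 per arm, the expected understatement of a true 10% risk is 0.42 to 1.85 points. The figure near 5 points needs both 4 of 20 stopped and a threefold hazard, and should be read as an extreme illustration. All of these are small beside the sampling error of an arm of 20: Table 12 of the Protocol gives 1.2% to 31.7% for 2 events. The case for changing the text is that the rules contradict each other and the loss is avoidable, not that a large bias has been shown.

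**What to change.** Reconcile 7.2.1 with 4.7 and 8.2.2. State that every participant who received at least one dose and has not withdrawn consent continues SAE, AESI and MAAE ascertainment, by visit or call, through 12 months after their own last vaccination, and that the PSRT's discretion covers additional visits and not a shorter period.

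Leave unchanged the rules for stopping vaccination and the existing provisions for pregnancy (7.2.2), HIV (7.3), withdrawal of consent (7.3.2) and incarceration (8.2.11.4).

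As an optional companion, SAP Section 7 could name the denominator for late events and report, by arm, how many participants completed the 12 months. That would make any remaining loss visible.

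The cost is a short edit to 7.2.1 and, for a few participants, visits or calls that the planned schedule already contains.

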7.2.2. Pregnancy

Subjects who become pregnant post investigational product administration will not receive any additional investigational product. The subject will be followed for safety to term by phone interview and laboratory assessment.

7.3. Participant Discontinuation/Withdraw from the Study

A participant may withdraw from the study at any time at his/her own request, or may be withdrawn at any time at the discretion of the investigator for safety, behavioral, or administrative reasons. Reasons may include the following:

- Repeated failure to comply with protocol requirements
- Recommended withdrawal by the study investigator, e.g., because of worsening health status, intercurrent illness, or AEs interfering with study assessments as determined by the investigator
- Participant requests withdrawal.

If the participant withdraws consent for disclosure of future information, the sponsor's representative may retain and continue to use any data collected before such a withdrawal of consent. If a participant withdraws from the study, he/she may request destruction of any samples taken and not tested, and the investigator must document this in the site study records. Participants who acquire HIV will be discontinued from study vaccinations, and additional research blood draws will not be performed. However, the participant will continue with safety assessments: pregnancy test, CBC with differential, and Creatinine/ALT.

Refer to the schedule of activities in [Table 1](#) for data to be collected at the time of study discontinuation and follow-up and for any further evaluations that need to be completed.

7.3.1. Replacement of Withdrawn Participants

Participants who withdraw or are withdrawn from study vaccinations or the study completely, or are lost to follow-up after signing the ICF and administration of the study product will be replaced if enrollment is still open. If a participant withdraws from the study or discontinues vaccination before all slots have been filled, the vacated randomization slot will be filled with the next available participant. Participants who did not receive the study injection will not count toward the total participants enrolled in the study.

7.3.2. Follow-up for Participants Who Withdraw Consent

After withdrawal of consent, the study team will engage in no further communication with the participant except as directed by an IRB and/or USAMRDC regarding information concerning participant safety.

7.4. Lost to Follow-up

A participant will be considered lost to follow-up if he or she repeatedly fails to return for scheduled visits and is unable to be contacted by the study site.

The following actions must be taken if a participant fails to return to the clinic for a required study visit.

The site must attempt to contact the participant and reschedule the missed visit as soon as possible and counsel the participant on the importance of maintaining the assigned visit schedule and ascertain whether or not the participant wishes to and/or should continue in the study.

- In cases in which the participant is deemed lost to follow up, the investigator or designee must make every effort to regain contact with the participant (where possible, three (3) telephone calls and, if necessary, a certified letter to the participant's last known mailing address or local equivalent methods). These contact attempts should be documented in the participant's medical record.
- Should the participant continue to be unreachable for 3 months, he/she will be considered to have withdrawn from the study with a primary reason of lost to follow-up.

8. STUDY ASSESSMENTS AND PROCEDURES

Study procedures and their timing are summarized in Section 1.3, Schedule of Activities.

All screening evaluations will be completed and reviewed to confirm that potential subjects meet all eligibility criteria. The investigator will maintain a screening log to record details of all subjects screened and to confirm eligibility or record reasons for screening failure, as applicable.

The maximum amount of blood collected from each subject during the study will not exceed 550 mL per 8 weeks. Blood will be collected into vacutainer tubes according to standard operating procedures. Substitution of tube types may be made as long as the substitution does not interfere with the study performance. A 10% variance in blood volume is acceptable, in case of an error or a broken or clotted vial.

8.1. Safety Assessments

8.1.1. Demographic/Medical History

Age, sex at birth, gender identity, date of birth, birthplace, level of education, occupation and baseline medical history of participants will be recorded. Participant's medical conditions, previous procedures, medications, and history of abnormal laboratory values, if available, will be recorded in the participant's medical history.

8.1.2. Physical Examination

For the purpose of assessing AEs, symptoms and directed medical examination will be performed based on the medical judgment of the investigator. In addition, participants will be asked to record their temperature and complete a diary card at home in the evening after the vaccination and each evening thereafter for a total of 14 days. Study staff will provide thermometers and participants will be trained how to complete the diary card, use the thermometer, and to measure injection site induration and redness using the ruler after each vaccination.

Investigators will pay special attention to clinical signs related to previous serious illnesses.

